#### 9.2.3 Consent for the donation of residual semen samples for Biomedical Research

Patients who are eligible to take part in the trial will also be eligible to have any residual semen samples remaining after the ICSI procedure and mechanistic evaluations donated to the Human Biomaterials Resource Centre (HBRC) Biobank, University of Birmingham. Participation within the HBRC Biobank will be discussed with couples at the same time as discussing their participation in the HABSelect trial. Verbal and written details (the Donation of Human Tissue for Research Patient Information Sheet) will be provided to patients. Following information provision, patients will be given as long as they need to consider participation (a minimum of 24 hours is recommended) and will be given the opportunity to discuss the biobanking of any residual semen sample after all the HABSelect procedures are completed with their family and other healthcare professionals.

Patients who wish to have residual semen samples stored for the HBRC Biobank will be asked to sign The University of Birmingham Donation of Human Tissue for Research consent form. As for the main trial, a record of consent to this biobanking, detailing the date of consent and all those present will be kept in the patients notes. One copy (University of Birmingham Donation of Human Tissue for Research) of consent form will be transferred to the HBRC, one copy filed within the Investigator Site File and the third copy of the consent form will be given to the participant.

## 9.3 Screening

Participating research sites will be required to complete a screening log of all couples who were recommended ICSI procedure as a method of choice for egg fertilisation during their fertility treatment. The screening log will be used to indicate whether couples are eligible for the trial based on their assessment according to trial inclusion/exclusion criteria or if they decline participation. Anonymised information will be collected including:

- age
- date screened
- which treatment cycle they are currently undergoing

AND

• reason if not eligible for trial participation

OR

reason for declining participation despite eligibility (only with participants agreement)

OR

• other reason for non-enrolment

Screening information will be entered into the secure electronic database or sent directly to PCTU trial coordinator when requested.

## 9.4 Enrolment

Following written informed consent, participants will be enrolled into the study by a delegated member of staff at the trial research site. At the point of enrolment the couple will be issued a unique ID number and recorded on the trial enrolment log.

Participants may only be enrolled into the trial by an authorised member of staff at the trial research site, as detailed on the Site Research Staff Delegation Log.

A unique ID number will consist of the trial site code (site ID) and followed by the consecutive screening number starting with 001 (please also refer to section 11.10.3 and Appendix 2).

After trial registration the research site will:

- Complete the trial enrolment log
- Add the unique couple participant ID number to all CRFs
- Ensure that participants are notified of their appointment dates.

#### 9.5 Randomisation Procedures:

Following screening and formal enrolment onto the study, confirmation of eligibility and completion of baseline assessments the female participant will commence egg stimulation and the couple will enter the IVF clinical care pathway. At the couples' visit for the IVF procedure, approximately 2-8 weeks following enrolment, couples will be randomised into the trial. The time interval between enrolment and randomisation is centre dependent as they will be following local practice for egg simulation which precedes IVF. Couples will be randomized 1:1 to interventional (PICSI) and the non-interventional (PVP-ICSI) arms. Randomisation into the study will be typically on the day of the ICSI/PICSI and will be performed by an authorised member of staff at the research site, using the web 24-hour automated randomisation system developed by PCTU. Each centre will be provided with a unique set of log-in usernames and passwords for the study staff to do this. Online randomisation is available 24 hours a day, 7 days a week apart from short periods of scheduled maintenance. The randomisation system will generate intervention arm allocation to the couple which will be recorded on the Randomisation and Intervention Form.

### 9.6 Randomisation method and stratification variables

Randomisation will be achieved using a computer-generated minimisation algorithm that includes a random element to ensure treatment groups are well-balanced for the following participant characteristics, details of which will be required.

- maternal (<35, ≥35) age,
- paternal (<35, ≥35) age,
- number of previous miscarriages (0,1-2, >2),
- hormonal indicator of ovarian reserve: FSH (<6.0, ≥6.0miU/ml) or AMH (<17.0, ≥17.0 pmol/L) when FSH is not available

Due to logistical constraints minimisation will not include HBS.

Minimisation factors will be balanced separately within each centre.

The person randomising the participant will have to enter the couple's unique ID number, allocated at trial enrolment onto randomisation service website in order to receive the intervention allocation for that couple.

#### **10. TRIAL INTERVENTION**

#### 10.1 Trial intervention with PICSI dishes and Hydak slides

The investigational products are the PICSI sperm-selection dish and the Hydak, hyaluronan binding score slides, both marketed (in the UK) by Biocoat, USA. Both products are CE marked and approved for clinical use. Full details can be found on the Origio and the Biocoat web sites. Regardless of the randomised allocation, HBA scores (HBS) will be obtained from all semen samples from both the interventional (PICSI) and the non-interventional (PVP-ICSI) arms using the Hydak slide. Only the interventional arm will make use of the PICSI plates.

#### 10.2 Application

The protocol makes no additional requirements of the couple undergoing IVF treatment. Normally, density gradient washed and prepared motile sperm are selected for ICSI. This is achieved by adding the sperm suspension to PVP on an inverted microscope. Sperm motility is slowed sufficiently to allow capture by the experienced embryologist who then immobilises the sperm by crushing its flagellum with the injection pipette. The sperm is then taken up into the injection pipette and injected directly into the egg. In the interventional arm, exactly the same procedure is carried out except that the washed and prepared motile sperm are allowed to interact with the PICSI substrate to immobilise the sperm first. There are no other interventions.

## 10.3 Packaging, and supply of PICSI plates, Hydak slides and PVP

As already indicated, the PICSI plates and Hydak slides will be sterile packed and supplied by Origio (UK) Ltd, directly to the participating clinic on a pro-rata basis based on estimated recruitment targets and under the auspices of the TMG. Reserve stocks will also be held at the sponsor site for distribution as and when required.

At study initiation, the central trial team in collaboration with site staff will arrange an initial supply (equivalent to three months) of the products under test to the trial sites. The receiving clinics will confirm receipt of the products.

#### **10.4 Participant Intervention**

Couples will follow the guidance and procedures required for IVF preparation according to the centre involved (which as NHS units follow standard ICSI procedures – with the quality control assessment provided by UKNEQAS). For standard ICSI, it is normal practice for eggs to be

injected with sperm a few hours after egg collection. The embryologist or andrologist will prepare the semen samples by density gradient (DG) washing. Couples will then be randomised into one of the two arms and the prepared sperm will be processed through either modified (PICSI) or standard (PVP-ICSI) procedures by the embryologist. The operating procedures for PICSI and PVP-ICSI will be standardised across centres and integrated into their SOP Quality Management Systems as required by Human Fertilisation and Embryology Authority (HFEA). Prepared (pelleted) sperm samples will be used to obtain hyaluronan binding score (HBS). Injected eggs will be incubated overnight to allow pronucleate zygotes (PNZ) to form by Day 1. Once all ICSI procedures, including HBA scoring have been completed on Day 0, any remaining sperm sample will be processed according to Section 11.8.1 for the mechanistic research evaluation.

#### 10.5 Subject Withdrawal

By consenting to participate in the trial, couples are consenting to the initial baseline screening for eligibility, trial intervention, follow-up and data collection. Couple or individual partner participants may withdraw consent from the trial at any time without explanation. Alternatively, participants may be withdrawn if in the opinion of the investigator or the care providing clinician or clinical team, it is medically necessary to do so. If a couple or either partner explicitly states their wish to withdraw from the trial, Pragmatic Clinical Trial Unit (PCTU) should be informed by completion of End Report CRF.

#### 10.5.1 Participant withdrawal before intervention

i.e. post enrolment and prior to randomisation will not receive the trial intervention and will resume standard treatment/care. Participants who withdraw prior to randomisation or trial intervention will be replaced with another couple on the trial.

#### 10.5.2 Participant withdrawal after intervention

Withdrawal from follow-up is the decision of the participant. As there is no difference in the follow-up monitoring of intervention versus non-intervention arms, we do not anticipate couples choosing to withdraw following embryo transfer. However we acknowledge withdrawal from the follow-up is the decision of the participant and occasionally such situations may occur.

Participant withdrawal post randomisation (after intervention) is categorised as follows:

Withdrawal of consent but the couple/participant is willing for clinical data to be collected on pregnancy outcome but not for any further mechanistic assessments to be undertaken. Data collected to this point may be used.

• Withdrawal of consent for the trial follow-up schedule but the participant is willing

to have any information already collected to be utilised.

• Withdrawal of consent for follow-up information to be used and refusal of data already collected to be utilised.

Study personnel will make every effort to obtain and record information about the reasons for discontinuation and to follow-up the women for all safety and efficacy outcomes, as appropriate. To make a clear distinction as to exact participants' preferences we will use a withdrawal of consent form. If a participant explicitly withdraws consent to have any data recorded their decision will be respected and recorded on the electronic data capture system. All communication surrounding the withdrawal will be noted in the participant's records and no further Case Report Forms (CRFs) will be completed for that participant.

# 11. SCHEDULE OF ASSESSMENT, SAMPLE & DATA COLLECTION

PROCEDURE	Pre- treatment (CRF1)	Hormonal treatment phase (CRF2)	Treatment phase (CRF3-4)			Pregnancy follow- up & outcome (CRF5-7)			Sperm mechanistic assessment
TIMELINES	Referral to Fertility Centre Referral – Day 21 of female menstruation	21 days after the day 1 of female menstruation – 36 hours after hCG stimulation	Day 0	Day 1	Day 2-5	Day 714	Week 6-9	End of pregnancy	6 months after study recruitment commencement
Screening									
Eligibility assessment	X								
Informed Consent and enrolment to the study	X								
Baseline assessments for both partners	X								
Female - history of fertility treatment, gynaecological disorders and previous pregnancies	X								
Male – history of previous fertility treatment; general medical history and current medication	X								
Hormonal profile (AMH/FSH)	X								
Type of hormonal treatment		X							
Gametes collection & randomisation to the study			X						
Sperm profile (volume, sperm concentration, % forward progressive motility, % abnormal cells)			X						

HBS		X						
Number of aliquots		X						
ICSI / PICSI		X						
Number of			Х					
pronucleozygotes								
Number of				Х				
embryos								
transferred								
Biochemical					Х			
pregnancy								
assessment (hCG								
level)								
Clinical						Х		
pregnancy								
Fetal sac presence						Х		
& number or fetal								
heartbeat								
Miscarriage							Х	
(gestational age)								
Live Birth							Х	
(gestational age)								
Adverse Events							Х	
Sperm analysis	II							
Cytology								X
Comet								X
Tunel								X
HALO								X
Acridine Orange								X
CMA3								X
Aniline Blue								X

### **11.1 Clinical Assessments**

#### 11.1.1 Completion of Baseline Assessments (refer to Schedule of Assessment table)

Baseline Assessment will consist of the following information:

#### **BOTH PARTNERS**

- 1. Formal trial eligibility criteria assessment (inclusion/exclusion criteria)
- 2. Baseline demographic data (age, height, weight, BMI and ethnicity)

3. History of smoking, alcohol, recreational drugs use

## FEMALE

- 4. Pre-treatment hormonal assessment
- 5. History of previous fertility treatment
  - a. number of treatment cycles
  - b. year
  - c. partner (if different)
  - d. type of treatment
  - e. outcome of treatment (pregnancy outcome if any)
- 6. History of previous natural pregnancies (if available) including:
  - a. year
  - b. partner (if different)
  - c. biochemical and clinical pregnancy assessment
  - d. pregnancy outcome
- 7. Gynaecological & general medical history
  - a. gynaecological disorders (i.e. polycystic ovaries syndrome, endometriosis etc.)
  - b. gynaecological surgeries (if any)
  - c. general medical history and current medication

## MALE

- 8. Male semen assessment prior to current treatment (if available).
- 9. General medical history and current medication

## **11.1.2** Completion of CRF related to semen characteristics and gamete transfer.

At the end of Day 0, Intervention CRF will be completed on the online database by the delegated staff member. CRF will capture semen sample assessment (that details the sperm sample characteristics such as: sample sperm concentration before processing, % forward progressive motility, % abnormal forms etc.). The Embryo Transfer CRF will be completed on day 2-5 after embryo transfers have been completed to capture pertinent data (per couple) on whether PNZs formed, whether a transfer took place and how many embryos were transferred. The PCTU trial coordinator and CI will have access to the whole online database and will monitor CRF completion.

### 11.2 Clinical Assessments post intervention

Following the IVF procedure couples will resume standard IVF/ante-natal care and have no further scheduled trial-specific follow up. However the couples participating in the HABSelect trial will have their unique ID number linked to the female partner's patient records so that the routine fetal/pregnancy outcome data can be periodically captured and entered onto the CRF. IVF follow-up is relatively standard throughout the country and concerns the mother only who will be tested for biochemical pregnancy 7-14 days after embryo transfer. If the biochemical pregnancy test is positive, a scan will be performed looking for a fetal sac or heartbeat at 6-9 weeks after embryo transfer. These two outcomes are normally recorded in the patient notes and will be recorded on the trial CRF. If clinical pregnancy is confirmed the woman will be transferred from IVF to standard antenatal care for all further follow up of pregnancy. Beyond this point, patient records will be monitored as required to capture any pregnancy loss (a routinely recorded event), or record of a live birth; these outcomes will be transferred onto the appropriate HABSelect CRF by the research nurse or another appropriately trained staff member allocated to the study as they become available.

### **11.3 Outcome Data Collection:**

- Biochemical pregnancy rates based on the detection of hCG in the mother's blood or urine.
- Clinical pregnancy rates based on ultrasound scanning (fetal sac and/or detection of heartbeat).
- For the primary clinical outcome: successful live birth ≥37 completed weeks since embryo transfer or last menstrual period.
- For the secondary clinical outcomes:
  - miscarriage, defined as pregnancy loss after confirmation of clinical pregnancy
  - live birth <37 weeks

All of the above will be based on data gathered from the ICSI cycle with first fresh embryo transfer per couple.

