#### Intervention Phase

- Four equal aliquots obtained from the remainder of the semen sample
- Initial Sperm concentration
- HBS score
- Number of pronucleate zygotes formed
- Number of embryos transferred
- Biochemical pregnancy indicators
- Clinical pregnancy indictors (as confirmed by USG scan)

Post Intervention Phase:

- Successful live birth ≥37 completed weeks since embryo transfer or last menstrual period.
- Clinical pregnancy rate based on detection of fetal heartbeat or presence of fetal sac at 6-9 weeks' gestation
- Miscarriage rates defined as pregnancy loss at any time post confirmation of

clinical pregnancy

- Live births at < 37weeks' gestation.
- Serious adverse events

All of the above will be based on data gathered from the ICSI cycle with first fresh embryo transfer per couple.

Extra

- Additional Information/Note to File CRF
- Final Study Status /Early Withdrawal CRF

CRFs will be pseudonymised using couple unique ID allocated during enrolment. This code will consist of the trial site code followed by consecutive numbers starting at 001. Site codes are documented in Appendix 2.

E.g.: Birmingham Women Fertility Centre (0119), couple number 1 (001): 0119/001

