### 13.1 Trial Outcomes

#### 13.1.1 Primary outcome measures:

### 13.1.1.1 *Clinical*:

Live birth at ≥37 weeks' gestation following the first fresh ICSI treatment

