## 13.1.2 Secondary outcome measures:

### 13.1.2.1 Clinical:

- Clinical pregnancy rate based on detection of a fetal heartbeat or the presence of fetal sac at 6-9 weeks' gestation
- Miscarriage, defined as pregnancy loss after confirmation of clinical pregnancy
- Live birth <37 weeks' gestation

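### Sections 11.3 and 11.10.3 let the 37-week primary outcome be counted from embryo transfer, which contradicts the definition in weeks of gestation used elsewhere in the protocol

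*Protocol*

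**What the plan says.** The protocol defines the primary outcome by gestation in the synopsis (Section 3), the primary clinical objective (6.1.1.1), the main endpoint (7.3), the primary purpose (7.6) and the outcome list (13.1.1.1), which reads "Live birth at ≥37 weeks' gestation following the first fresh ICSI treatment". The complementary secondary outcome in 13.1.2.1 is "Live birth <37 weeks' gestation".

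The two places that tell sites what to collect say something else. Section 11.3 has "successful live birth ≥37 completed weeks since embryo transfer or last menstrual period", and the post-intervention CRF list in 11.10.3 repeats it: "Successful live birth ≥37 completed weeks since embryo transfer or last menstrual period". Neither says which origin to use, or how to convert one to the other.

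Transfer takes place on Day 2 to 5, with ICSI on Day 0, according to the schedule in Section 11. Section 11.1.2 agrees: "The Embryo Transfer CRF will be completed on day 2-5 after embryo transfers have been completed". The same schedule lists gestational age as the item recorded for live birth and for miscarriage, but does not say how it is dated.

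Clinical pregnancy shows a similar mismatch. Section 11.2 states that "a scan will be performed looking for a fetal sac or heartbeat at 6-9 weeks after embryo transfer", whereas 13.1.2.1 (with 6.1.2.1, 11.10.3 and 13.2.2) places the outcome at 6 to 9 weeks of gestation: "Clinical pregnancy rate based on detection of a fetal heartbeat or the presence of fetal sac at 6-9 weeks".

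**The concern.** Embryo transfer and last menstrual period are more than two weeks apart, so the threshold moves with the origin. A site that follows the transfer limb literally would record a birth at, say, 38 weeks of gestation as not meeting the primary outcome. If the secondary outcome is dated the same way, that birth would also be recorded as a live birth before 37 weeks.

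Outcomes are abstracted from routine records at many centres (11.2, 11.10.3, 13.4.1), so local habits could differ. At stake are the number of primary events, and with it the power, and a clean split between the primary outcome and the under-37-week secondary outcome. For early losses, two scan windows on different clocks leave it unclear whether a loss between them counts as no clinical pregnancy or as a miscarriage. Section 5.4.3 names fewer early losses as a main expected benefit.

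**Working it through.** **The plan's own figure.** Section 13.5 gives 3,266 couples for a 5-point improvement at 90% power. The protocol does not state the control rate beside that number; 24%, the average live birth rate in 5.4.4, reproduces it. Two-sided 5% is assumed, in line with the 95% confidence interval in 13.2.1. Allocation is 1:1 (9.5).

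n per arm = (1.960 + 1.282)² × (0.24×0.76 + 0.29×0.71) / 0.05² = 10.507 × 0.3883 / 0.0025 ≈ 1,632.01, rounded up to 1,633, so 3,266 in total. The sample size is not in question.

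**The gap between the clocks.** 37 weeks = 259 days. Assume 14 days from last menstrual period to egg collection; this is a convention that the protocol does not state. Gestation at 37 weeks after transfer = 259 + 14 + transfer day:

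- Day 2: 275 days = 39w2d; births from 37w0d to 39w1d are affected.
- Day 3: 276 days = 39w3d; births to 39w2d are affected.
- Day 5: 278 days = 39w5d; births to 39w4d are affected.

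The gap is 16 to 19 days. The schedule in Section 11 starts the hormonal phase 21 days after day 1 of menstruation, before Day 0. If that period were taken as the last menstrual period, the gap would be at least 21 + 2 to 21 + 5 = 23 to 26 days.

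**The scan window.** Six to nine weeks after transfer = 42 + 16 to 63 + 19 = 58 to 82 days, or 8w2d to 11w5d of gestation. This overlaps a window of 6 to 9 weeks of gestation by less than a week.

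**Effect on power.** Let q be the share of births at ≥37 weeks of gestation that fall in the gap, and s the share of records dated from transfer. Both rates are multiplied by f = 1 − q×s. With n = 1,633 per arm and p̄ the mean of the two rates:

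power = Φ{[|p₂−p₁|√n − 1.960√(2p̄(1−p̄))] / √(p₁(1−p₁)+p₂(1−p₂))}

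With f = 1 this gives 90.0%. For q = 0.4:

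| s | rates | power |
|---|---|---|
| 0.25 | 21.6% v 26.1% | 85.5% |
| 0.5 | 19.2% v 23.2% | 79.9% |
| 1 | 14.4% v 17.4% | 65.0% |

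Over s = 0.25, 0.5 and 1, power is 88%, 86% and 80% for q = 0.2, and 83%, 73% and 46% for q = 0.6. The protocol gives neither q nor s.

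**Effect on the odds ratio** (the planned measure, 13.2.1). As planned: (0.29/0.71)/(0.24/0.76) = 1.29. With q = 0.4 and every record dated from transfer: (0.174/0.826)/(0.144/0.856) = 1.25. For q = 0.3 and 0.5 it is 1.26 and 1.24.

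**The case against.** The strongest reply is that the schedule of assessments already asks for gestational age at live birth and at miscarriage, and that every governing definition says gestation. If sites enter gestational age from maternity notes, the 37-week cut can be applied centrally and nothing is misclassified. This stands, and it limits the exposure to records that were in fact dated from transfer. It does not remove the problem, because 11.3 and 11.10.3 are the only text that says how the 37 weeks are counted, and they permit transfer.

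The phrase could also be read as meaning that either clock is enough. The last-menstrual-period limb would then always be met first and the transfer limb would do no work; the text does not say so. A statistical analysis plan, not seen here, may hold the derivation, but it cannot recover the origin if sites entered only completed weeks or yes/no.

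Three stronger readings are tempting and not supported:

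- *That power falls to 57% to 74%.* At 3,357 followed up, those figures need every record at every site to be dated from transfer, with 30% to 50% of births in the gap. They are upper-bound scenarios.
- *That the treatment comparison is biased.* Follow-up staff are blinded (7.5, 11.10.3), so the error should not differ by arm, and the odds ratio moves little.
- *That centres become non-comparable in a way that undermines the trial.* Minimisation is balanced within centre (9.6) and the primary model adjusts for centre (13.2.1).

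On the scan, 11.2 describes when a routine scan is done, and a woman with one scan is classified by what it shows. That part is a mismatch to reconcile, with no size attached.

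**Conclusion.** The contradiction is real and sits in the two places that govern data capture for the primary outcome. Under the 14-day convention the transfer clock moves the threshold to between 39w2d and 39w5d, so any record dated that way turns births from 37w0d to at least 39w1d into primary failures.

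How much this costs depends on two shares that the protocol does not give. With 40% of births in the gap, power falls from 90% to about 86% if a quarter of records are affected, and to 65% if all are. The harm is lost events and power, with some blurring of the primary and under-37-week outcomes. There is no sign of bias toward either arm, and the sample size calculation is sound. This should be fixed, but it does not by itself invalidate the endpoint, because the intended meaning can be recovered from the other sections.

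**What to change.** In 11.3 and 11.10.3, replace the two-origin phrase with live birth at ≥37+0 weeks of gestation under one stated dating rule. One example is gestational age in days = delivery date − egg collection date (Day 0) + 14. Apply the same clock to the under-37-week outcome and to the dating of losses. Reconcile the scan timing in 11.2 with the clinical pregnancy window in 6.1.2.1, 11.10.3, 13.1.2.1 and 13.2.2, so that clinical pregnancy and miscarriage share that clock.

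Confirm that the CRF captures the delivery date, or gestational age together with its dating origin, so that the outcome can be derived centrally. The CRF content in 11.10.3 does not list a delivery date. For records already entered, query the origin.

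The cost is a short wording change, CRF guidance and possibly one added field. No extra couples or visits are needed.
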